2.4.4 Research Biopsies

After obtaining informed consent, patients with solid tumors will undergo a mandatory tumor biopsy at screening, while optional biopsies are collected only upon patient consent. Patients

who have had a mixed tumor response will have biopsies of two lesions that have had different responses, if deemed safe and possible.

Patients will undergo 3-6 core biopsies mandatory at screening and optional on Week 4 and upon disease progression. An optional FNA core will be collected at screening, Week 4 and upon disease progression. FNA and cores will be used for molecular profiling, including RNA sequencing, DNA sequencing, and RPPA, and PDX generation.

If a patient is having a planned surgery or diagnostic procedure they will not have tumor biopsy. Instead residual tissue from the surgery or diagnostic procedure will be collected.

2.4.5 Tumor Analysis

We will use biopsies obtained for research studies for assessment for putative markers of response/progression as described below. In addition, when archival tissue is available, we will test archival tumor samples from patients with unusual responses or rapid progression to targeted therapies. Whenever available, frozen tissue will be used. When possible, if more than one sample is available, the most recent sample or the sample that corresponds to the site in which the response was observed will be prioritized for molecular characterization. However, where possible, samples from multiple sites if available will be compared to determine the molecular heterogeneity between sites that could contribute to unexpected responses. Archival tissue will only be used if the pathology collaborators determine that archival tissue can be used for research, while reserving adequate archival tissue for patient care needs.

The technologies used to characterize the tumor will depend on availability of frozen tumor, and specimen amount available. The technologies to be used is likely to evolve over the next few years, thus we will use state of the art and emerging technologies to comprehensively characterize the tumors from unusual responders. Findings identified with non-CLIA technologies will be verified with CLIA approaches as they become available.

2.4.6 DNA Sequencing

Whenever possible, tumor DNA will be analyzed along with normal tissue DNA from the same patient in order to determine what somatic mutations are present in the tumor.

Mutation status of key oncogenes including NF1, KEAP1, NRF2, and STK11/LKB1 pathway genes will be evaluated. The candidate genes will be assessed for target resequencing of genomic areas of interest, SNP genotyping, and copy number variation analysis through a combination of approaches. This could either be PCR or capture based selection of candidate genes.

Next generation sequencing is newer technology that allows for massive parallel sequencing, that is high-throughput, with decreased time and cost of sequencing. When frozen tumor is available, selected tumors from patients who have had dramatic responses (partial or complete responses or rapid progression), will be characterized in depth with next-generation sequencing. Exome sequencing, or full genomic sequencing will be performed. As technology becomes available, this will be extended to FFPE tissue. Samples may also be sent to commercial partners (eg Myriad, Foundation Medicine or Asuragen) for high-throughput candidate gene testing. Commercial collaborators will be blinded to patient identifiers.

2.4.7 Reverse Phase Proteomic Arrays (RPPA)

When samples are available from responders as well as non-responders to allow for comparison, we will also assess activation status of key cell signaling pathways by functional proteomics.

We hypothesize that differences in functional proteomic profile may be associated with clinical benefit from targeted therapies. RPPA is a quantitative, sensitive, and reproducible proteomic technology. RPPAs involve the ‘dot’ array of lysates on nitrocellulose-coated slides and thus it is essential that using antibodies be validated as monospecific. The assays will quantitated using analysis of total and phosphopeptides and standard cell lysates placed on each slide.

2.4.8 Transcriptional Profiling of RNA

We hypothesize that RNA expression signature of tumor tissue collected at baseline, during treatment and upon progression may predict clinical benefit from targeted therapies. RNA expression signature will be assessed when samples are available from responders as well as non-responders to allow for comparison.

Tissue will be macrodissected and total RNA isolated using a Qiagen protocol. An Illumina sequencing library will be generated using an Illumina RNA Exome library preparation kit. Samples will be sequenced on an Illumina NovaSeq instrument, yielding approximately 7 million reads per sample. Sequencing reads will be matched to a collection of human transcripts. Logarithm of the normalized number of the matching reads will be used as a measure of the corresponding gene expression. Only genes with large enough counts of matching reads will be used in the analysis. We estimate that about 15,000 genes will be analyzed.

2.4.9 PDX Models

To explore mechanisms of resistance of *NFI*-aberrant tumors to glutaminase inhibition using pre- and post-treatment tumor biopsies obtained from patients treated on a clinical trial of Telaglenastat (CB-839) HCl, and patient-derived xenograft (PDX) models.

CLIA certified molecular profiling is required for study entry. We will enroll patients into the different baskets. The primary end-point is radiographic response. If there are 4 or more responses out of the total sample of 27 patients, we will conclude that the treatment is worthy of further consideration. This optimal Simon two-stage design with a one-sided type-I error rate of 5% provides 88% power to compare a null response rate of 5% and an alternative response rate of 25%. Patients will undergo matched pre- and post-treatment (week 4 and upon progression) biopsies that will be used to elucidate pharmacodynamic changes and adaptive responses by transcriptome and proteomic (RNAseq and RPPA) analyses. These changes will be correlated with response to treatment. The *in vitro* studies will inform the studies performed on these clinical samples. Finally, PDX models will be developed from tumor specimens obtained from patients with treated on this or other studies. These new models will provide an opportunity to test the effects of possible new drug combinations designed to overcome Telaglenastat (CB-839) HCl resistance.

3. PATIENT SELECTION

3.1 Eligibility Criteria

3.1.1 Patients must have histologically confirmed malignancy that is metastatic or unresectable.

3.1.2 Patient must have histopathologic confirmation of advanced solid tumor with NF1 mutation, NF1 mutant MPNST, KEAP1/NRF2 mutant and STK11/LKB1 mutant tumors (Molecular profiling performed in any CLIA certified lab (Including tumor and cfDNA), eg. Caris, FoundationOne, FoundationAct, Oncomine, Guardant etc.)
NOTE: For all cohorts annotation for actionability will be performed by the PRECISION ONCOLOGY DECISION SUPPORT (PODS) TEAM SHEIKH KHALIFA BIN ZAYED AL NAHYAN INSTITUTE FOR PERSONALIZED CANCER THERAPY (PCT)
THE UNIVERSITY OF TEXAS MD ANDERSON CANCER CENTER
[name]
EMAIL: [contact]
WEBPAGE: <https://pct.mdanderson.org/#/>

3.1.3 Patient must have no standard therapies available.

3.1.4 Patient must be aged greater than 18 years old for all cohorts.

3.1.5 Patients for NF1 mutant MPNST and NF1 mutant non-MPNST cohorts must be ≥ 40 kg.

3.1.6 Patient must be at least 4 weeks since any prior surgery or radiotherapy.

3.1.7 Females of childbearing potential must have a negative serum pregnancy test (≤ 14 days) prior to start of trial treatment.

3.1.8 RECIST measurable disease and biopsiable targetable lesion.

3.1.9 Patients must have measurable disease, defined as at least one lesion that can be accurately measured in at least one dimension (longest diameter to be recorded for non-nodal lesions and short axis for nodal lesions) as ≥ 20 mm (≥ 2 cm) by chest x-ray or as ≥ 10 mm (≥ 1 cm) with CT scan, MRI, or calipers by clinical exam. See Section 12 for the evaluation of measurable disease.

3.1.10 Patients with treated brain metastases are eligible if there is no evidence of progression for at least 4 weeks after CNS-directed treatment, as ascertained by clinical examination and brain imaging (MRI or CT) during the screening period.

3.1.11 HIV-infected patients on effective anti-retroviral therapy with undetectable viral load within 6 months are eligible for this trial.

3.1.12 ECOG performance status ≤ 2 (Karnofsky $\geq 60\%$, see Appendix A).

3.1.13 Patients must have normal organ and marrow function as defined below:

- leukocytes	$\geq 3,000/\text{mcL}$
- absolute neutrophil count	$\geq 1,000/\text{mcL}$
- platelets	$\geq 100,000/\text{mcL}$
- total bilirubin	$\leq 1.5 \times$ institutional upper limit of normal (ULN) and up to 3 mg/dL for patients with Gilbert's disease
- AST(SGOT)/ALT(SGPT)	$\leq 3 \times$ institutional ULN and $\leq 5 \times$ institutional ULN for patients with liver metastases
- creatinine	\leq institutional ULN, as age appropriate OR
- glomerular filtration rate (GFR)	$\geq 30 \text{ mL}/\text{min}/1.73 \text{ m}^2$ for patients with creatinine levels above institutional normal.

3.1.14 The effects of Telaglenastat (CB-839) HCl on the developing human fetus are unknown. For this reason and because anti-metabolic agents like Telaglenastat (CB-839) HCl are known to be teratogenic, women of child-bearing potential and men must agree to use adequate contraception (hormonal or barrier method of birth control; abstinence) prior to study entry and for the duration of study participation. Should a woman become pregnant or suspect she is pregnant while she or her partner is participating in this study, she should inform her treating physician immediately. Men treated or enrolled on this protocol must also agree to use adequate contraception prior to the study, for the duration of study participation, and 4 months after completion of Telaglenastat (CB-839) HCl administration.

3.1.15 Ability to understand and the willingness to sign a written informed consent document.

3.2 Exclusion Criteria

3.2.1 Patients who have had chemotherapy or radiotherapy within 4 weeks (6 weeks for nitrosoureas or mitomycin C) prior to entering the study.

3.2.2 Patients who have not recovered from adverse events due to prior anti-cancer therapy (*i.e.*, have residual toxicities $>$ Grade 1).

3.2.3 Patients who are receiving any other investigational agents.

3.2.4 History of allergic reactions attributed to compounds of similar chemical or biologic composition to Telaglenastat (CB-839) HCl.

3.2.5 Patients with glioma will be excluded.

3.2.6 Patients with active or prior history of hepatitis B or C will be excluded.

3.2.7 Telaglenastat (CB-839) HCl is a weak *in vitro* inhibitor of CYP2C9. Therefore, patients receiving any medications or substances that are substrates of CYP2C9 are eligible, but should use caution with substrates that have a narrow therapeutic index. Because the lists of these agents are constantly changing, it is important to regularly

consult a frequently-updated

medical reference. As part of the enrollment/informed consent procedures, the patient will be counseled on the risk of interactions with other agents, and what to do if new medications need to be prescribed or if the patient is considering a new over-the-counter medicine or herbal product.

- 3.2.8 Uncontrolled intercurrent illness including, but not limited to, ongoing or active infection, symptomatic congestive heart failure, unstable angina pectoris, cardiac arrhythmia, or psychiatric illness/social situations that would limit compliance with study requirements.
- 3.2.9 Pregnant women are excluded from this study because Telaglenastat (CB-839) HCl is *anti-metabolic* agent with the potential for teratogenic or abortifacient effects. Because there is an unknown but potential risk for adverse events in nursing infants secondary to treatment of the mother with Telaglenastat (CB-839) HCl, breastfeeding should be discontinued if the mother is treated with Telaglenastat (CB-839) HCl.

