2.2.5 Clinical Safety Summary

NCI Protocol #: 10220
Version Date: January 3, 2025

As of January 23, 2018, 161 patients have received Telaglenastat (CB-839) HCl as monotherapy, and 250 patients have received Telaglenastat (CB-839) HCl in combination with other agents in phase 1 and early phase 2 trials (Investigator's Brochure). Among 59 patients who received Telaglenastat (CB-839) HCl monotherapy on the TID (fasted) schedule over a dose range of 100-1000 mg, two dose limiting toxicities

(DLTs) have been observed: one at 250 mg TID (grade 3 elevated creatinine) and one at 400 mg TID (grade 3/4 elevated liver function tests (LFTs)). No DLTs have been reported on the monotherapy BID (fed state) schedule up to a dose of 800 mg. DLTs reported in combination cohorts have been: Grade 4 neutropenia (400 mg BID with 80 mg/m² IV paclitaxel weekly for three weeks in every four week cycle and 400 mg BID with 4 mg once daily (QD) pomalidomide for 21 days out of every 28 day cycle and 40 mg each week (QW) of dexamethasone), grade 3 pruritic rash (400 mg BID with 10 mg everolimus QD), grade 3 alanine aminotransferase (ALT) increase (800 mg BID with 240 mg IV nivolumab once every two weeks), and grade 4 platelet count decrease (600 mg dose with 60 mg cabozantinib QD). Although a maximum tolerated dose (MTD) has not been defined for either monotherapy or combination therapy, 800 mg BID is the highest dose that is confirmed to be safe and well tolerated in single-agent and combination Telaglenastat (CB-839) HCl studies. The 800 mg BID dose also exhibits robust exposure and pharmacodynamics effects, and has been declared recommended Phase 2 Dose (RP2D).

The largest monotherapy study of Telaglenastat (CB-839) HCl (CX-839-001) included 120 patients, 32 receiving between 100 to 800 mg of Telaglenastat (CB-839) HCl TID without food and 88 receiving between 600 to 1000 mg of Telaglenastat (CB-839) HCl with food (Investigator's Brochure). On the BID schedule, 72.7% of patients experienced an AE, the most common of which were fatigue, elevated LFTs, gastrointestinal AEs, and photophobia. These AEs were typically grade 1/2, reversible, and manageable without dose interruption or modification. Grade 3 LFTs were significantly reduced (2.3% of patients) on the BID schedule. One grade 3 AE of anemia was also considered to be related to Telaglenastat (CB-839) HCl.

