6. TREATMENT PLAN

6.1 Agent Administration

Treatment will be administered on an outpatient basis. Reported adverse events and potential risks are described in Section 10. Appropriate dose modifications are described in Section 7. No investigational or commercial agents or therapies other than those described below may be administered with the intent to treat the patient's malignancy.

This phase 2 basket clinical trial utilizes single agent CB 839 HCl at the recommended phase 2 dose at 800 mg (Table 2 and 3).

Table 2. Treatment Plan for Telaglenastat (CB-839) HCl as a single agent	
Category	Treatment Plan
Telaglenastat (CB-839) HCl agent dose	800 mg
Telaglenastat (CB-839) HCl administration and schedule	Telaglenastat (CB-839) HCl dose by mouth twice daily, approximately 12 hours apart, immediately after a meal on day 1 to day 28, repeated every 28 days
Duration of treatment	Repeated every 28 days until unacceptable toxicity or disease progression. Refer to Section 6.3 for additional stopping criteria.
Duration of the study	Upon completion of follow-up procedures.
Duration of follow-up	Every 3 months (\pm) 14 days after the last administered treatment dose

If patient develop toxicity then the dose can be reduced as per Table 3.

Table 3. Dose Reductions of Telaglenastat (CB-839) HCl	
Dose Level	Telaglenastat (CB-839) - HCl Dose

Starting dose	800 mg BID
First dose reduction	600 mg BID
Second dose reduction	400 mg BID
Third dose reduction	Discontinue Telaglenastat (CB-839) HCl

The patient will be requested to maintain a medication diary of each dose of medication. The medication diary will be returned to clinic staff at each clinic visit.

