7. Radiologic evaluation (CT or MRI or PET-CT) will be performed at screening within 28 days prior to C1D1, every 2 cycles (8 weeks), ± 7 days, for the first 13 cycles, then every 3 cycles (12 weeks) ± 7 days and EOT.
8. Tumor measurement: Per RECIST v1.1 for solid tumors and per Modified RECIST (Byrne and Nowak 2004) for pleural mesothelioma. Tumor measurements are repeated every 2 cycles (every 8 weeks) ± 7 days, for the first 13 cycles, then every 3 cycles (12 weeks) ± 7 days and EOT. Documentation (radiologic) must be provided for patients removed from study for progressive disease.
9. Tumor-specific markers, such as CA19-9, CA-125, CEA, PSA, etc. will be tested at the time with radiologic evaluation.
10. Whole blood sample for oncometabolomics and pharmacokinetics will be collected on Day 1 and Day 15 prior to drug administration and after drug administration at 0.5, 1, 2, 4, and 8 hours. In addition, oncometabolomics will be collected on Week 4 (C1D22) post Telaglenastat (CB-839) HCl dose. All "prior to drug administration" samples should be collected after at least 8 hours of fasting (the patient must not eat or drink anything but water). All "after drug administration" samples should be collected after patients are dosed with Telaglenastat (CB-839) HCl immediately after a meal.
11. Optional whole blood sample for exploratory genetic and biomarker testing for cfDNA and WES/RNASeq will be collected at screening, at C1D22, C2D22 and disease progression (EOT) for patients who are consented for such analysis under fasting conditions.
12. Tumor Biopsy: Tumor biopsy at screening are required for all patients for exploratory analyses. In addition, archival tissue samples will be collected if available. Optional on-treatment biopsy will be collected on week 4 (C1D22 ± 3 days) and upon disease progression at EOT. Coagulation tests must be performed and evaluated prior to all biopsy procedures. Patients are consented for tumor biopsy.
13. Telaglenastat (CB-839) HCl dose by mouth twice daily, immediately after a meal on continuous dose from day 1 to day 28-day cycle.
Dosing may occur prior to, during, or after the clinic visit, according to the patient's usual administration schedule.
14. For patients with $\geq SD$ for at least 13 cycles who are on a steady dose for ≥ 2 cycles, study assessments may be reduced to every 3 cycles (i.e., at Cycles 16, 19, 22, etc.) and 3 cycles worth of study medication can be provided at clinic visits.

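### The entry washout covers only chemotherapy and radiotherapy, and the baseline scan need not follow the last prior dose, so shrinkage from an earlier drug can be counted as a telaglenastat response

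*Combined protocol and SAP*

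**What the plan says.** Four provisions of the protocol govern earlier or concurrent treatment.

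- Section 3.2.1 excludes "Patients who have had chemotherapy or radiotherapy within 4 weeks (6 weeks for nitrosoureas or mitomycin C) prior to entering the study".
- Section 3.1.6 adds: "Patient must be at least 4 weeks since any prior surgery or radiotherapy".
- Section 3.2.3 excludes "Patients who are receiving any other investigational agents". It is in the present tense and has no look-back.
- Section 6.1 applies once protocol treatment is running: "No investigational or commercial agents or therapies other than those described below may be administered" with intent to treat the malignancy. It does not address time since the last earlier dose.

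Two further criteria bear on the point. Section 3.2.2 excludes "Patients who have not recovered from adverse events due to prior anti-cancer therapy", meaning residual toxicity above Grade 1. Section 3.1.3 reads: "Patient must have no standard therapies available". It does not require progression on the last treatment.

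On imaging, footnote 7 of the Study Calendar (section 11) says that radiologic evaluation "will be performed at screening within 28 days prior to C1D1". Section 12.1.3 asks for baseline evaluations as near the start of treatment as possible and at most 4 weeks before it. Neither ties the scan to the end of earlier treatment. Under 9.4.2 and 12.1.1 everyone who takes one dose is evaluable for response, and 12.1.4.3 counts best response from the start of treatment.

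**The concern.** The parenthesis on nitrosoureas and mitomycin C suggests that 3.2.1 means cytotoxic drugs. The next criterion, 3.2.2, uses the wider term prior anti-cancer therapy, so a broader term was at hand and 3.2.1 does not use it. On that reading, a patient who has just stopped a kinase inhibitor, antibody, checkpoint inhibitor, hormonal agent or investigational drug meets the entry criteria. The baseline scan may have been taken while that drug was still being given.

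Tumour shrinkage that began under the earlier drug would then be measured from a pre-shrinkage baseline and recorded after C1D1. There is no control arm to reveal this, and no planned analysis separates recently treated patients from the rest. Each cohort is judged on a handful of responses. One response is enough to pass the futility stop, and it is a quarter of the four needed to call the drug worthy of further study.

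**Working it through.** **Inputs** (section 9.1): n1 = 9, stop if 0 respond; n = 27, success if 4 or more respond; null rate 0.05; alternative 0.25. The documents give neither the share of patients with recent unlisted therapy nor the chance that such a patient shows a carry-over response.

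**Step 1: reproduce the stated design.** P(success) = sum over x = 1 to 9 of P[Bin(9, p) = x] × P[Bin(18, p) ≥ 4 − x].

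- At p = 0.25: 0.881 (stated 88%).
- Early stopping at p = 0.05: 0.95^9 = 0.630 (stated 63%).
- Expected enrolment: 9 + 18 × (1 − 0.630) = 15.7 (stated 15.7).
- At p = 0.05: 0.2985 × 0.0581 + 0.0629 × 0.2265 + 0.0077 × 0.6028 + 0.0006 = 0.0369. The stated 5% is a ceiling, which this discrete design respects.

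**Step 2: one certain carry-over responder, all others at 5%.**

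- In stage 1: the futility stop cannot trigger, and 3 more responses are needed from 26. P[Bin(26, 0.05) ≥ 3] = 1 − 0.2635 − 0.3606 − 0.2372 = 0.139.
- In stage 2: stage 1 must still yield a response, and the other 17 stage-2 patients supply the rest. The sum over x ≥ 1 of P[Bin(9, 0.05) = x] × P[Bin(17, 0.05) ≥ 3 − x] is 0.0620 + 0.0366 + 0.0084 = 0.107.

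**Step 3: a general lift in the apparent null rate.**

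| Apparent rate for an inactive drug | P(success) |
|---|---|
| 5% | 3.7% |
| about 5.5% | 5.0% |
| 7% | 9.9% |
| 8% | 14.2% |

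**Step 4: what those rates would require.** Let f be the share recently treated with an unlisted class and c the chance of a carry-over response in such a patient. Both are assumptions. The apparent rate is 0.05 + 0.95 × f × c. The 5% ceiling is passed once f × c exceeds (0.0552 − 0.05)/0.95 = 0.0055.

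| f | c | P(success) for an inactive drug |
|---|---|---|
| 10% | 5% | 4.9% |
| 10% | 10% | 6.2% |
| 20% | 10% | 9.5% |
| 30% | 10% | 13.5% |
| 50% | 20% | 50.1% |

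**Step 5: a milder version of step 2.** If a cohort has only a 10% chance of containing one stage-1 carry-over responder, P(success) is 0.9 × 0.0369 + 0.1 × 0.1386 = 0.047, still inside 5%.

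**The case against.** Several safeguards narrow the route.

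- A patient still responding to a standard drug would hardly satisfy 3.1.3.
- A partial response needs a fall of at least 30% from baseline. The first on-study scan comes about 8 weeks after C1D1 by the Study Calendar (section 12.1 says 12 weeks), and 12.1 asks for a confirmatory scan at least 4 weeks after a response is first documented. Carry-over from a stopped drug would have to produce that fall and hold it.
- In a patient who is progressing at entry, an early baseline scan works against telaglenastat, because growth before C1D1 raises the later measurements.
- Chemotherapy is not defined, so a site might read it as all systemic therapy.
- Eligibility is verified before registration (4.3.2) and treatment may start up to 28 days later (4.4), so a patient who has just stopped an investigational agent may in practice have a longer gap.

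All of this limits how often carry-over could occur, and none of it closes the gap. Progression on the last therapy is not required, no minimum interval is set, and confirmation shows that shrinkage lasts without showing which drug caused it. If sites read chemotherapy differently, that is itself a reason to fix the wording.

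A reader might also infer a safety finding from the combination dose-limiting toxicities in 2.2.5, such as "grade 3 alanine aminotransferase (ALT) increase (800 mg BID with 240 mg IV nivolumab once every two weeks". The documents do not support that. Those events arose under co-administration, which 6.1 bars, and they say nothing about a drug already stopped. Section 3.2.2 screens out unresolved toxicity above Grade 1 from any prior anti-cancer therapy, 3.1.13 sets blood-count, liver and renal limits, and adverse events are tabulated by attribution. Misattributed toxicity is at most a minor part of this point.

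**Conclusion.** The gap is in the text, and it should be closed. As written, the plan allows shrinkage from an earlier drug to be counted as a telaglenastat response, and the two-stage rule is sensitive to single responses: 3.7% false-positive probability at a true 5%, against 13.9% or 10.7% with one certain carry-over responder in stage 1 or stage 2.

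It would go too far to conclude that carry-over is being credited to telaglenastat, or that the real error rate is 10% to 14%. Those figures are conditional on a carry-over response having occurred. The documents do not say how often that would happen, and under low assumed frequencies the rate stays below 5%. The conclusion rests on the narrower reading of chemotherapy in 3.2.1 and on the absence of any other interval in the protocol. It does not rest on the safety data.

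**What to change.** - **Eligibility wording.** Align 3.2.1 with the wider term that 3.2.2 already uses, so that it covers all prior anti-cancer therapy, and give 3.2.3 a look-back. The intervals are for the sponsor to set.
- **Baseline scan.** In the Study Calendar and 12.1.3, require the baseline tumour scan to be taken after the last dose of any prior anti-cancer therapy.
- **Patients already enrolled.** For each responder, list the last prior therapy and its stop date. Add a sensitivity analysis of the primary endpoint that counts as non-responders those whose baseline scan preceded that stop date.

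The sample size and decision rule do not change. The cost is amended wording, a listing and one extra analysis. A few patients may start later or need a repeat baseline scan.
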